7. STATISTICS AND DATA ANALYSIS

Sample size calculations:

Aims 1 and 2 are observational, thus sample size is opportunistic and pragmatic.

Aim 1: Approximately 4 wheezers/month undergo bronchoscopy, with recruitment over 24 months and based on past experience, a conservative 60% acceptance rate for inclusion, we estimate 50 children will be included in Aim 1.

Aim 2: Based on previous data, a sample size of 44 participants (assuming 25% positive cases) will allow the detection of a moderate level of agreement, with expected sensitivity at 67% (95%CI: 23%-95%), at a significance level of 5% with 80% power. Children for Aims 2 and 3 need to be recruited in the first 2 years to allow 12 months follow-up. From the number of preschool wheezers seen in the clinic, we estimate recruitment of 4 children per month, allowing approximately 100 children to be included in Aim 2 over 24 months.

Aim 3: 20% of families agreed to be included in a previous interventional trial undertaken by the [name] group, therefore n=15 is my target for Aim 3. An important outcome of Aim 3 will be to understand how many agree to be included and reasons for declining, this will enable a realistic sample size calculation for a future interventional clinical trial. A sample size of 15 participants will allow the detection of a high level of agreement, with expected sensitivity at 95% (95%CI: 45%-100%), and at a significance level of 5% with 80% power.

Data Analysis:

Aim 1

To assess the diagnostic accuracy of aeroallergen sensitisation and blood eosinophils in reflecting lower airway eosinophils; of blood neutrophil phenotype and chemotaxis in mirroring lower airway neutrophils; and of induced sputum and oropharyngeal swabs in replicating lower airway infection, I will compute several accuracy measures, such as sensitivity, specificity, positive and negative predictive values, and positive and negative likelihood ratios. Furthermore, to verify the validity of the standard cutoff and to eventually identify more appropriate cutoff values for the considered diagnostic tests, I will perform Receiver Operating Characteristic (ROC) curve analysis.

Aims 2 and 3

Information related to the feasibility of the intervention will be gathered using a combination of quantitative and qualitative methods. Descriptive statistics will be used to summarise the baseline demographics of all patients included in the feasibility analysis and to evaluate parental and children's satisfaction with the various diagnostic tests. To identify factors responsible for dropout, baseline characteristics and questionnaire scores of patients who agreed or did not agree to undergo follow-up will be compared using parametric and non-parametric tests, where appropriate.

To understand the robustness of the proposed diagnostic approach, I will investigate the temporal variation in biomarker trajectories and their relation to clinical status by adopting longitudinal generalised linear models and dynamic Bayesian networks (dBNs). Bayesian networks (BN) are probabilistic graphical models that, using Bayes' theorem, represent knowledge about a certain domain/disease by encoding conditional dependences among random variables in directed acyclic

graphs. A dBN is the extension of a BN applied to longitudinal data. The model describes the dependencies among the variables over time. This allows for encoding cycles and feedbacks between variables to represent their relationships over different time windows. The heterogeneity of the joint dynamics of wheeze recurrence and biomarker variation will be explored using joint latent class models for recurrent events, which will allow me to identify subgroups of children characterised by different disease risk profiles linked to specific biomarker variations. The groups are formed to minimise the within-class variability both with respect to the evolution of longitudinal markers and to the occurrence of an event.

To identify differences between patients in the intervention study compared to those in the observational arm, I will perform differential longitudinal analysis. I will combine simple parametric and nonparametric hypothesis testing techniques with time-varying models based on time-series analysis and smoothing splines. Symptom scores will be recorded using a validated questionnaire at each visit for those in the intervention study and adjustments will be made for season.

Data and all appropriate documentation will be stored for a minimum of 10 years after the completion of the study, including the follow-up period.

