These newly described pathological preschool wheeze clusters, based on blood and airway inflammation and infection, suggest that a biomarker guided treatment approach may prove more successful than current standard care in preventing preschool wheeze attacks. My project aims to extend these findings to bedside clinical tests that can be used for targeted treatment. I will investigate the feasibility, sensitivity, specificity, and longitudinal variability of 1. skin prick tests (to detect allergen sensitisation), 2. blood eosinophils (using a point-of-care test), 3. blood neutrophil function (using a chemotaxis assay and flow cytometry), 4. bacterial detection (pathogen specific PCR from oropharyngeal and nasal swabs) and induced sputum, and 5. lung function with bronchodilator reversibility (forced oscillation technique [FOT]), as biomarkers that can be applied in future stratified interventional clinical trials.

Proposed non-invasive biomarkers:

1. Non-invasive tests for allergic sensitisation and eosinophilia

The previous analyses identified that 25% of wheezers were in the atopic cluster, and both observational and clinical trial data have identified atopy (aeroallergen sensitisation) and blood eosinophilia as biomarkers of preferential response to ICS⁷. Based on the known action of ICS targeting eosinophilia, I propose that ICS would be an appropriate treatment for children in the atopic cluster. This suggests every preschool wheezer who is considered for ICS treatment should have phenotyping with aeroallergen sensitisation and blood eosinophil as a minimum before a decision is made to commence ICS.

Skin prick tests for allergen sensitisation are simple, non-invasive and can be performed in clinic. However, performing blood test in preschool children is challenging. Venepuncture is a difficult procedure in this age group, time consuming and the result is not immediately available, and

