Biomarkers and treatment to prevent wheeze attacks in preschool children without allergic sensitisation / blood eosinophilia remain elusive. The [name] group have obtained preliminary data showing that the phenotype of airway neutrophils is distinct in the different preschool wheeze clusters. Wheezers as a group had a predominance of $CD62L^{hi}$ regulatory neutrophils, however only those **without** bacterial infection had significantly more $CD62L^{hi}$ neutrophils. Those with bacterial infection in their airways had significantly more $CD62L^{lo}$ inflammatory neutrophils (Figure 2). A flow cytometry panel has been established in the lab to phenotype neutrophils from 200mcl of blood taken during finger prick sampling, and I will use this to relate blood-derived data to lower airway neutrophil phenotyping in order to identify peripheral biomarkers of neutrophil activation status.

[figure not shown]

Figure 2. Proportion of CD62L⁺ neutrophils in bronchoalveolar lavage (BAL) from preschool wheeze (W) compared to non-wheeze related disease (NWRD), and wheezers with (+) and without (-) airway bacterial infection.

The [name] lab has also investigated the **function of blood neutrophils** with the use of TAXIScan chemotaxis apparatus which allows dynamic measurements of leukocyte migration with as few as 500 cells/data point. The assay generates a rich data set regarding the migration of individual neutrophils along a gradient of chemoattractant. Analysis of the cell tracks allows measurement of the velocity (V) and directionality (D) of each cell and to combine this in a V-D plot. Setting relevant threshold values for both parameters directional migration amongst the population of neutrophils can be accurately measured. Using this assay, preliminary data show reduced chemotaxis of blood neutrophils to CXCL8 from preschool wheezers compared to healthy controls (Figure 3).

[figure not shown]

Figure 3. Chemotaxis of blood neutrophils from preschool healthy controls (PHC) compared to preschool wheezers (PSW) to CXCL8. (A) reduced % chemotaxis, (B&C) cell tracks towards CXCL8.

In this study, using small 100 μ L blood samples, I will correlate neutrophil function and phenotype with infection status, clinical symptoms, and prescribed medication in children with recurrent preschool wheeze.

3. Non-invasive tests for airway bacterial infection

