Preschool wheeze Cluster 3 (non-atopic, high infection rate) had the highest prevalence of airway bacterial and viral infection, and *Moraxella catarrhalis*, *Haemophilus influenzae* and *Streptococcus pneumoniae* made up 80% of the bacteria identified, suggesting these children may benefit from targeted antibiotics. Induced sputum testing is feasible and safe in young children but is time consuming and requires specialist training. However, a pathogen specific PCR to detect these three bacteria is also available. Bacterial detection in induced sputum, or by PCR, may be an additional biomarker for stratification of targeted antibiotic treatment. It has been shown that oropharyngeal swabs reflect lower airway microbes in children with different chronic lung diseases and nasopharyngeal samples also reveal *Moraxella catarrhalis*, *Haemophilus influenzae* and *Streptococcus pneumoniae* as the commonest organisms in preschool children's respiratory systems during wheeze episodes.

Preliminary data from the [name] group comparing the pathogen specific PCR in oropharyngeal swabs to broncho-alveolar lavage (BAL) PCR and BAL culture results have shown complete agreement between BAL culture and oropharyngeal swab PCR. *Additional* organisms were detected by the PCR compared to culture in 26/64 (41%) samples, and the PCR failed to detect a cultured organism in 3/64 (4%) patients. This suggests that the PCR test is accurate, and I propose that throat and nasal swabs will prove to be feasible as non-invasive tests to detect lower airway bacterial infection and identify children who may benefit from targeted antibiotics.

4. Lung function tests to assess airway obstruction and bronchodilator reversibility (BDR)

For recurrent wheezers without atopy, peripheral eosinophilia, or airway infection, the treatment of choice may be as required bronchodilators and/or regular long-acting muscarinic antagonists. However, to understand the benefit of these treatments, lung function testing and demonstration of bronchodilator reversibility is required. The [name] group have generated preliminary data in fifteen preschool children showing feasibility of the forced oscillation technique (FOT), a recognised test for airway function, and have demonstrated BDR (Figure 4). However, feasibility in a larger number and for longitudinal assessments needs to be determined.

[figure not shown]

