Figure 4: Correlation between respiratory resistance at 8 Hz (R8) z-score obtained using the forced oscillation technique and blood eosinophils using finger prick testing (%) in preschool children aged 1-5 years.

Research question:

Can non-invasive tests (biomarkers) of allergen sensitisation, eosinophilic inflammation, phenotype and function of airway neutrophils, airway infection and lung function be used to personalise therapy for recurrent preschool wheeze?

Hypothesis:

Non-invasive biomarkers are stable, feasible to measure longitudinally, with high sensitivity and specificity, and can be used to personalise therapy of recurrent preschool wheeze.

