Aim 1: Children participating in this aim are recruited from the cohort of preschool wheezers who have been identified by their existing clinical teams as needing a bronchoscopy, as part of their standard clinical management. We will aim to use surplus samples taken during the bronchoscopy and endobronchial biopsy for the study, with parental consent. Number of children: 50.

Aim 2: Children participating in this aim are recruited from the respiratory clinics who meet the criteria listed below. Children recruited for Aim 1 can be recruited into Aim 2. Number of children: 100

Aim 3: Children participating in this aim can be recruited from Aims 1 or 2, as this is a small proof-of-concept study to investigate biomarker-driven targeted therapy for preschool wheeze. Number of children: 15

Duration:

Over 36 months, with each child being followed-up for 12 months after recruitment.

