3.1. STUDY OUTCOME MEASURES

Primary outcomes:

Specificity, sensitivity, longitudinal stability and acceptability of non-invasive tests (biomarkers) of allergen sensitisation, eosinophilic inflammation, phenotype and function of airway neutrophils, airway infection and lung function (FOT) in objective phenotyping of preschool wheeze and investigating the relationship between these objective tests and symptom control (TRACK questionnaire) and wheeze attacks.

Secondary outcomes:

Relationship of the tests below to wheeze attacks and symptom control, using the respiratory and asthma control in kids (TRACK): a caregiver-completed validated questionnaire for preschool-aged children, 3 monthly for a year.

1. Lung function (Rrs: respiratory system resistance; Xrs: respiratory system reactance; AX: area of reactance) 3 monthly
2. Inhaled corticosteroid dose and oral prednisolone dose 3 monthly
3. Induced sputum cultures at baseline and 12 months
4. Blood eosinophil count 3 monthly
5. Neutrophil function and phenotype in relation to infection status, clinical symptoms, and prescribed medication
6. Nasal and oropharyngeal swab for infection 6 monthly
7. Assessment of symptom burden to caregivers using the validated Paediatric Asthma Caregivers Quality of Life Questionnaire: PACQLQ

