6. ASSESSMENT AND FOLLOW-UP

Children participating in Aim 1: One-off assessment carried out on the day of the bronchoscopy and no follow-up needed. Assessments carried out are listed below in Table 4. We will aim to do the oropharyngeal swab, skin prick testing (if not done in the last 6 months) and finger prick blood test under general anaesthetic, during the bronchoscopy procedure.

A bronchoscopic programme which enables research samples to be collected, with parental informed consent, from children undergoing clinically indicated bronchoscopy for severe recurrent wheeze is established at the Royal Brompton Hospital. The [name] group have shown that it is safe to take additional samples and this does not add significant time.

Table 3: Assessments and investigations for Aim 1 only:

Assessments/ Investigations	Study visit
Vital Signs measurements (Temp, BP, Pulse and respiration)	X
Height and weight	X
Physical Examination	X
Medical History	X
Informed consent	X
Validated symptom questionnaire (TRACK)	X
Paediatric Asthma Caregivers Quality of Life Questionnaire: PACQLQ	X
Forced oscillation technique and bronchodilator reversibility test	X
Oropharyngeal and nasal swabs for pathogen specific PCR to detect Moraxella/Streptococcus/Haemophilus	X
Skin prick test or blood aeroallergen IgE (house dust mite, cat, dog, grass, tree pollen and mixed moulds)	X

Sputum induction for bacterial culture and pathogen specific PCR to detect Moraxella/Streptococcus/Haemophilus	X
Blood sample collection (Finger prick) for point of care testing and laboratory studies	X
Bronchoscopy – bronchoalveolar lavage and endobronchial biopsy (part of routine clinical management and surplus sample used for study with parental consent)	X

Children participating in Aim 2 and Aim 3: Children in these two aims do **not** need bronchoscopy. They will have the panel of non-invasive tests listed in Table 5, at the intervals below. These children will be seen for the research study at the same time as their routine outpatient clinic follow-up visits, which will be every three months over one year (Visits 1-4), and therefore no separate research visits are required. The tests listed below in Table 5 will be undertaken at the times indicated.

Table 4: Assessments and Investigations for Aims 2 and 3.

Assessments/ Investigations	Study visits (every 3 months for 12 months)				
	Baseline	1	2	3	4
Vital Signs measurements (Temp, BP, Pulse and respiration)	X	X	X	X	X
Height and weight	X	X	X	X	X

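### Aim 1 plans to search for new ROC cut-offs with no selection rule and no optimism correction, so sensitivity and specificity at those cut-offs will tend to be overstated

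*Combined protocol and SAP*

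**What the plan says.** Section 7 (Data Analysis, Aim 1) plans sensitivity, specificity, both predictive values and both likelihood ratios for the non-invasive tests against lower-airway findings. It then adds ROC analysis "to verify the validity of the standard cutoff and to eventually identify more appropriate cutoff values for the considered diagnostic tests". It gives no criterion for picking a cut-off (Youden, a target sensitivity or another) and no bootstrap, cross-validation or split sample. The rest of section 7 deals with Aims 2 and 3 and adds nothing on this. The plan does not say that accuracy at a ROC-derived cut-off will be the headline result, nor that it will not be.

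The reference sample comes from Aim 1 alone. Section 6 describes Aim 1 as a "One-off assessment carried out on the day of the bronchoscopy and no follow-up needed", and says that Aims 2 and 3 need no bronchoscopy. Section 3 notes that "Children recruited for Aim 1 can be recruited into Aim 2", but this brings no new reference sample.

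On existing thresholds:

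- **Blood eosinophils.** The only numeric patient-level cut-off is 0.3 × 10⁹/L, in Table 5 for Aim 3. It is not identified as the standard cut-off meant in Aim 1.
- **Neutrophil chemotaxis.** Section 1.2 says "Setting relevant threshold values for both parameters directional migration amongst the population of neutrophils can be accurately measured". These are settings for single cells, given without numbers, and not a cut-off that classifies a child.
- **Bacterial PCR.** Section 1.2 says "a pathogen specific PCR to detect these three bacteria is also available", so the result is read as detected or not.

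Section 3.1 lists as primary outcomes "Specificity, sensitivity, longitudinal stability and acceptability of non-invasive tests (biomarkers) of allergen sensitisation" and the other marker groups. The hypothesis in section 1.2 is "Non-invasive biomarkers are stable, feasible to measure longitudinally, with high sensitivity and specificity".

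**The concern.** A cut-off picked because it separates these particular children well fits their chance variation as well as the real signal. Sensitivity and specificity read off at that point, in the same children, are therefore too high on average. The effect is largest when one of the two groups is small, as reference-positives may be among 50 children.

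The bias runs towards the study's hypothesis and affects a primary outcome. Section 1.2 presents the tests "as biomarkers that can be applied in future stratified interventional clinical trials", so inflated figures and an unstable cut-off could be carried forward. No treatment in the present study depends on a ROC-derived cut-off.

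The markers affected are blood neutrophil phenotype and chemotaxis, where ROC is the only source of a patient-level cut-off that the plan names, and blood eosinophils if they are re-cut. Accuracy at a cut-off fixed beforehand is not affected. Nor are tests read as positive or negative: sensitisation, culture and PCR.

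**Working it through.** **1. Sample size.** The plan's accrual inputs give 4 per month × 24 months × 0.60 = 57.6 children, against a stated 50 (50/96 = 52% acceptance). The stated 50 is used here. Using 58 changes little: at 25% positives and AUC 0.7–0.8, a Youden cut-off overstates sensitivity by 10–11 points.

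**2. Inputs not in the documents.** These are the AUC, the marker distribution, the selection rule and, for neutrophil markers, the share of reference-positives. Section 1.2 gives about 25% for airway eosinophilia with sensitisation (0.25 × 50 = 12.5, so 12). The range was widened to 17 and 25 positives.

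**3. Model.** The marker is normal with SD 1 in both groups. The mean is 0 in reference-negatives and d = √2 × Φ⁻¹(AUC) in reference-positives. The cut-off either maximises Se + Sp − 1 (Youden) or minimises (1 − Se)² + (1 − Sp)² (closest to the corner). Optimism is the apparent value minus the true value at the chosen cut-off c, where true Se = 1 − Φ(c − d) and true Sp = Φ(c). There were 10,000 replicates per setting, AUC 0.6 to 0.9 and three tie rules. The Monte Carlo standard error of the sensitivity bias was at most 0.14 points.

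**4. Overstatement in percentage points (minimum to maximum over AUC, rule and ties).**

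| Positives of 50 | Se, midpoint cut-off | Sp, midpoint cut-off | Se, cut-off at an observed value | Sp, cut-off at an observed value |
|---|---|---|---|---|
| 12 | 7.5–13.8 | 2.3–4.3 | 9.0–14.8 | 1.3–3.3 |
| 17 | 5.7–10.6 | 2.8–5.5 | 7.0–11.7 | 1.9–4.4 |
| 25 | 3.9–7.7 | 4.0–7.6 | 5.1–8.6 | 2.9–6.7 |

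**5. Other rules.** If the rule requires observed sensitivity of at least 80%, sensitivity is overstated by 5.1–6.4 points (12 positives), 3.4–4.8 (17) and 2.0–3.1 (25). If it requires observed specificity of at least 80%, sensitivity is overstated by 0.9–2.7 points.

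**6. Worked example.** AUC 0.75, so d = 1.414 × 0.674 = 0.954; 12 positives, Youden, midpoint. Mean reported sensitivity is 77% against 65–66% true, a gap of about 12 points. The SD of the reported value is 16 points. The SD of reported minus true, the better yardstick, is about 11 points, close to the bias itself.

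**7. Control.** With the cut-off fixed at d/2 = 0.477, true sensitivity is Φ(0.477) = 68.3%, and the simulated mean is 68.4%. Fixing the cut-off removes the bias.

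**8. Intervals.** Exact 95% intervals for sensitivity at the searched cut-off covered 93–97% (midpoint) or 91–96% (observed value). They are wide: 8 of 12 gives 35% to 90%. The damage is mainly to the point estimate.

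**9. Does correction help?** A bootstrap that repeats the selection in each of 200 resamples removed 55–76% of the sensitivity bias. It left 2.8–5.7 points (12 positives), 2.0–3.7 (17) and 1.0–2.9 (25), and 0.7–2.0 points for specificity. At AUC 0.75 with 12 positives, root mean squared error for sensitivity fell from 15.6 to 12.8 points.

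**The case against.** The strongest reply is that the harm is conditional. The ROC step follows the main accuracy analysis and reads as an addition to it, and several tests cannot be affected. This stands, and limits the point to neutrophil markers and re-cut eosinophils.

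Second, the largest range uses a 25% share that the documents give for eosinophilic disease, while the markers most clearly affected are neutrophil markers. This also stands: 25 positives, with 4–8 points, is as compatible with the documents as 12 positives.

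Third, Youden and closest-to-corner are assumed, and a target rule does much less harm. That is true, and it is a reason to name the rule.

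Fourth, the plan's mention of a standard cut-off may cover neutrophil tests too. The documents do not rule this out, but they state no such value.

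Fifth, the hypothesis puts no number on high accuracy and Aim 1 has no success criterion, so the bias cannot by itself produce a formal false success. The work is developmental, and external validation remains possible. This limits the severity but does not make an uncorrected estimate of a primary outcome a good one.

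Sixth, the bootstrap is only a partial remedy, and imprecision from few positives remains. That is correct and should be said in the report. Even so, the corrected estimate had smaller total error in the settings examined.

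**Conclusion.** The concern holds. The plan provides for a cut-off search without a selection rule or internal validation, and the study has no other children in whom a searched cut-off could be tested against the lower airway.

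Under the stated model, with Youden or closest-to-corner selection at midpoints, sensitivity would be overstated by about 4–14 points, depending mainly on the number of positives, and specificity by about 2–8. Under a target rule the sensitivity figure is 1–6 points. The sensitivity bias was upward in every setting examined, as was the specificity bias under Youden and closest-to-corner selection. The size depends on the assumed AUC, normality, number of positives and rule; of the sizing inputs, only the 50 children and, as a guide, the 25% come from the documents. This should be corrected before analysis, but it does not threaten the study as a whole.

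**What to change.** In section 7, Aim 1:

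1. Name the criterion for choosing a ROC cut-off, and how ties are broken, before the data are examined.
2. Label every ROC-derived cut-off exploratory. Report its sensitivity and specificity with a bootstrap optimism correction that repeats the selection in each resample, next to the apparent values. State that the correction is partial.
3. Where a cut-off is fixed in advance, make accuracy at that cut-off the main result. State whether 0.3 × 10⁹/L is the standard cut-off for blood eosinophils, as an analysis threshold only.
4. Report AUC with a 95% confidence interval alongside sensitivity and specificity, not in their place.

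The cost is a few sentences and some analysis code, with no extra children, samples or visits. Reported accuracy at searched cut-offs will look somewhat less favourable.
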